1.2.4.2 Pre-clinical and Clinical Trials

Therapeutic studies in mouse models have shown that administration of antibodies blocking PD-1/PD-L1 interaction enhances infiltration of tumor-specific CD8+ T-cells and leads ultimately to tumor rejection, either as a mono-therapy or in combination with other treatment modalities. Anti-mouse PD-1 or anti-mouse PD-L1 antibodies have demonstrated anti-tumor responses as a mono-therapy in models of squamous cell carcinoma, pancreatic carcinoma, MEL and colorectal carcinoma. Blockade of the PD-1 pathway effectively promoted CD8+ T-cell infiltration into the tumor and the presence of IFN- γ , granzyme B, and perforin, indicating that the mechanism of action involved local infiltration and activation of effector T-cell function in vivo [22; 23; 24; 25; 26; 27]. Experiments have confirmed the in vivo efficacy of PD-1 blockade as a mono-therapy as well as in combination with chemotherapy in syngeneic mouse tumor models (see the Investigator's Brochure [IB]).

1.2.4.3 Pre-clinical and Clinical Trials

Ongoing clinical trials are being conducted in advanced melanoma, non-small cell lung cancer, head and neck cancer, urothelial tract cancer, triple negative breast cancer, gastric cancer, and hematologic malignancies. For trial details please refer to the Investigator's Brochure.

Pembrolizumab has been approved in melanoma and lung cancer.

1.3 Rationale for the Proposed Study

1.3.1 Rationale for Epigenetic Immune Priming (EIP):

Clinically, epigenetic immune regulation has been implicated in priming lung cancer cells to PD-1 inhibitors which resulted in prolonged responses^{3,4}. The efficacy of PD-1 inhibitors has not been established; however the expression of PD-L1 in ER+ breast cancer is low. PD-L1

expression however has been shown to be a poor predictor of survival and PD-L1 expression has been suggested to increase as ER+ tumors become resistant to therapy.

The role of epigenetic modulation has been studied extensively in breast cancer therapy. Several investigators have shown that HDAC inhibitors have immune modulatory functions, including modulation of Tregs, FoxP3 expression, changes in TIL expression, induction of PD-L1 expression and blockage of PD-1. We have previously shown that epigenetic modulation with an HDAC inhibitor can reverse hormone therapy resistance and force cells into programmed cell death¹. Based on these preclinical studies, we had proposed two clinical trials testing HDAC inhibitors with hormonal therapy in ER+ breast cancer.

We hypothesize that pre-exposure of breast cancer cells to the HDAC inhibitor vorinostat (i.e., Arm A, sequential treatment) will result in down regulation of T-regulatory cells (Tregs) and FoxP3, which will increase the efficacy of PD-1 inhibitors, as measured by ORR, and prime cells to increased immune response. We therefore anticipate the schedule of administration may play an important role in the administration of this combination strategy.

Recent preclinical studies have further suggested that epigenetic priming may be even more effective in ER-negative tumors that do not respond to Immune check point inhibitors or have low PD-1/PD-L1 expression. The goal of this study is to demonstrate that Vorinostat can increase PD-1 and PD-L1 expression.

1.3.1.1 Prior studies with vorinostat in breast cancer:

In a Phase II clinical trial, we evaluated the role of vorinostat (VOR) in reversing hormone therapy resistance in advanced breast cancer². In a single arm study, 43 patients (median age 56 years (31–71)) were treated. A total of 25 patients (58%) received prior adjuvant tamoxifen (TAM), 29 (67%) progressed on at least one prior chemotherapy regimen, 42 (98%) progressed after one, and 23 (54%) after two aromatase inhibitors. The objective response rate by RECIST criteria was 19% and the clinical benefit rate (response or stable disease \geq 24 weeks) was 40%. The median response duration was 10.3 months (confidence interval: 8.1–12.4). Histone hyperacetylation and higher baseline HDAC2 levels correlated with response and responses were mainly seen in the 56% of patients who had a meaningful change in acetylation with vorinostat. Preclinical studies have further suggested that hormonal therapy must be continued even in the presence of an HDAC inhibitor.

1.3.1.2 Prior studies with other HDAC inhibitors in breast cancer:

[figure not shown]
A second phase II (ENCORE 301) trial evaluated entinostat and exemestane, and treated patients with advanced estrogen receptor (ER)-positive breast cancer⁶⁶. This study recently received Breakthrough Therapy designation from the FDA for its potential to reverse resistance to hormonal therapies. The median PFS was 4.3 months versus 2.3 months, for entinostat and placebo, respectively (HR = 0.73; P = 0.06). The median overall survival in the combination arm was 28.1 m compared to 19.8 m in the exemestane arm (HR = 0.59; P = 0.036). The objective response rate to the combination was 6.3%, while to exemestane alone was 4.6% (P = 0.58). While these two studies cannot be compared directly, the preclinical studies and the clinical studies, as well as the current landscape of standard of care, will make the combination with tamoxifen more likely effective. The combination with tamoxifen will also allow enrollment of premenopausal women.

Hence the combination of HDAC inhibitors and PD-1 inhibitors may further result in an enhancement of anti-tumor efficacy of PD-1 inhibitors^{6,67}. Based on the established role of HDAC inhibitors in reversing hormone therapy resistance to antiestrogens and aromatase

inhibitors and the provocative role of HDAC inhibitors in modulating tumor immunity, we propose to test the role of epigenetic immune priming (EIP) in acquired hormone therapy resistance.

In a two arm Phase II trial, we will explore concurrent and sequential EIP testing two principles: Sequential priming with optimal immune activation (Arm A) and concurrent priming with maximal dosing of both epigenetic and immune modulators (Arm B).

Figure 1. Schematic of dosing schedule

2 Objectives of the Study

2.1 Primary objective:

- To define the optimal approach for epigenetic immune priming in hormone refractory breast cancer on the basis of overall response rate (ORR: CR+PR+SD at 24 weeks).
- Safety and tolerability of vorinostat, tamoxifen and pembrolizumab

2.2 Secondary objectives:

- To define the optimal approach for epigenetic immune priming in hormone –resistant breast cancer and ER-negative tumors
- To assess duration of response (DOR) 24 week landmark progression free survival (PFS:24)
- Median PFS and overall survival (OS)

- d) Tumor responses will also be calculated by Immune Related Response-Criteria (irRC).
- e) To test the response of tumor PD-L1 expression to epigenetic modulation

2.3 Exploratory objectives:

- a) To assess for post-treatment changes in tumor-infiltrating lymphocyte (TIL) populations, PD-L1 expression and potential indicators of response. If tumor samples demonstrate that epigenetic therapy converts tumors from a low (baseline) to high TIL (post-treatment) but without a corresponding increase in ORR, then we can confidently reject our hypothesis that enhancing TILs will increase pembrolizumab efficacy in this tumor type.
- b) Acetylation of histones in PBMCs as a pharmacodynamics response marker for vorinostat.

2.4 Endpoints

Two arm study to determine the role of sequential versus epigenetic priming of ER+ breast cancer cells.

A comparator arm in ER-negative tumors with biomarker endpoints

2.4.1 Primary Endpoints

- a) Overall response rate (CR+PR and SD at 24 weeks)
- b) Toxicity

2.4.2 Secondary Endpoints

- a) Duration of response rate
- b) 24 week landmark progression free survival (PFS:24),
- c) Median PFS and overall survival (OS),
- d) Tumor responses will also be calculated by Immune Related Response-Criteria (irRC)
- e) To test the response of PD-L1 expression to epigenetic modulation

2.5 Exploratory Endpoints

- To assess for post-treatment changes in TIL population, PD-L1 expression and potential indicators of response. If tumor samples demonstrate that the combination therapy converts tumors from a low (baseline) to high TIL (post-treatment) but without a corresponding increase in ORR, then we can confidently reject our hypothesis that enhancing TILs will increase pembrolizumab efficacy. Acetylation of histones in PBMCs as a response marker for vorinostat.

3 Study Design

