3.1 Characteristics

We propose a three arm, 20-87 patient trial in patients with hormone therapy resistant breast cancer to test the optimal sequence and dosing of epigenetic immune priming in hormone therapy resistant breast cancer. The two arms all include vorinostat, TAM and pembrolizumab to evaluate either sequential priming (Arm A) or, concurrent priming with maximal dosing of both epigenetic and immune modulators in ER+ (Arm B) and ER- (Arm C?) disease. Stage 1 of the trial will evaluate 20 patients, 10 in each arm and randomly assigned. If the response rates are adequate, the trial will proceed to Stage 2 in order to evaluate 58 patients, 29 in each arm.

Given the absence of responses in PD-L1 low patients to pembrolizumab, we will determine the benefits for vorinostat in reversing therapy resistance to pembrolizumab in ER-negative breast cancers (HER2-positive or negative)

Patients will be evaluated for response at 12 weeks by RECIST1.1 (using IR-RECIST) and will continue on therapy if they have stable disease or response at the time of disease evaluations. Patients with progression on imaging, but are clinically stable, may stay on study but will require follow up staging after 4-6 weeks. Patients will be assessed continually for safety and tolerability as well as for any adverse events. If progression on therapy with pembrolizumab, patient may continue if clinical indicated and be re-evaluated after 4-8 weeks.

We will follow AEs of clinical interest as defined by Merck and will dose modify pembrolizumab as per Merck guidelines. We have significant prior experience with vorinostat as an agent and are familiar with managing drug toxicities. In addition, we are experienced with immune-related toxicities as well.

Tissue biopsies of all patients will be collected prior to enrollment to assess for pre-treatment TIL and PD-L-1 expression. A limited number of patients with disease unamenable to biopsy will be allowed to enroll in the trial with prior approval from study PI. Follow up biopsies and peripheral blood collection will be taken from all patients post-treatment, prior to starting cycle 4, to characterize changes in local tissue effects and antigen-specific cellular and humoral immune responses in peripheral blood.

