3.6 Randomization Procedures

This is an open-label randomized trial; therefore, the Sponsor, investigator and subject will know the treatment administered. Two arms will be tested, with each independent assessment. Patients will be randomized to either arm using a computerized randomization program by [name]. Patients will be further stratified by prior number of chemo- and hormonal therapies.

No randomization is required for ER-negative patients (patients must have biopsiable disease)

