8.0 Statistical Considerations and Evaluation of Results

This trial will determine whether epigenetic priming may enhance the effects of PD-1 inhibitors in patients with ER+ metastatic breast cancer who have progressed on prior hormone therapy and chemotherapy. The trial will contain three arms. Within each arm we will determine whether epigenetic priming will required prolonged pre-exposure to epigenetic modulators or concomitant administration.

Three arms will be tested, with each independent assessment. Patients will be stratified by prior number of hormonal therapy and chemotherapy, then randomized across arms by [name], UCSF.

8.1 Response rates to chemotherapy in breast cancer are less than 20%. Historical response rates to pembrolizumab and MPDL3280A have been 18% and 19%, respectively, in patients whose tumors are PD-L1 positive. Hence, we expect the response rate for unselected patients and patients with no PD-L1 expression would be 10% or less. In contrast, we anticipate that vorinostat will increase the response rate to 30%**Sample Size and Power Estimate**

Response rates to hormonal therapy and MTOR or HDAC inhibitors have been reported as 5-20% (19% for VOR-Tam, 6% for entinostat-exemestane, 12% for exemestane-everolimus). Given the recent additions to hormonal therapy this trial will treat a patient population that has received more lines of therapy than these trials, however we are interested in an ORR of >30%.

8.2 For each arm: Using an Optimal Simon's two-stage design (Simon, 1989), the null hypothesis (H₀) that the true response rate is 10% will be tested against a one-sided alternative. In the first stage, 10 patients will be accrued and a decision will be made to continue or stop accrual based on the observed objective response rate (ORR). If there are 0 or 1 objective responses at 24 weeks in these 10 patients, accrual to this arm of the study will be stopped. Otherwise, 19 additional patients will be accrued for a total of n=29. We estimate that each regimen under evaluation will achieve ORR ≥ 30%. This study is designed to have an alpha of 0.0471, and a power of 80.5% to test the null hypothesis H₀: ORR = 10% against an alternative hypothesis, H_A: ORR = 30%, where ORR is defined as CR, PR, or SD ≥ 24 weeks where arms are enrolled independently.**Interim Analyses**

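### TIL conversion without a higher ORR cannot support confident rejection of the TIL hypothesis: the only reference is an assumed 10%, and no TIL–response test is specified

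*Combined protocol and SAP*

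**What the plan says.** The rule appears twice. Section 2.5 (Exploratory Endpoints) says that if the combination converts tumours from low to high TIL and ORR does not rise to match, "then we can confidently reject our hypothesis that enhancing TILs will increase pembrolizumab efficacy". Section 2.3 (Exploratory objectives) has the same sentence for epigenetic therapy, ending "then we can confidently reject our hypothesis that enhancing TILs will increase pembrolizumab efficacy in this tumor type". Neither place gives a TIL cut-point, the ORR from which an increase is measured, a test, an error rate or a margin.

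The rest of the plan bears on the rule as follows:

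- **Treatment.** In Table 5.1 both ER+ arms receive vorinostat, tamoxifen and pembrolizumab, and differ only in whether pembrolizumab starts in cycle 1 or cycle 2. Arm C receives vorinostat and pembrolizumab.
- **Comparison.** Section 3.6: "Two arms will be tested, with each independent assessment". In section 8, for each arm, the null hypothesis "that the true response rate is 10% will be tested against a one-sided alternative".
- **Source of the 10%.** Section 8 cites rates of 18% and 19% for two PD-1/PD-L1 inhibitors in PD-L1-positive tumours, infers 10% or less for unselected or PD-L1-negative patients, and anticipates 30% with vorinostat.
- **Definition of ORR.** CR, PR or SD at 24 weeks (sections 2.4.1, 8.2 and 8.3.2).
- **TIL analysis.** Section 8.3.4.1 summarises tissue immune subsets with descriptive statistics only. Its logistic model concerns PD-L1 and study arm, not TIL.
- **Repeat biopsy.** End of cycle 3 (Table 6, note f).

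**The concern.** The rule treats failure to see an increase as firm evidence that there is no effect. That would need a credible reference rate, a measure of TIL change attributable to priming, and enough precision to exclude a worthwhile effect. The plan secures none of the three for TIL.

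The repeat biopsy also falls after pembrolizumab has begun in every arm, so a TIL change cannot be credited to vorinostat alone. What is at stake is the mechanistic conclusion: a published statement that the TIL hypothesis has been refuted when the data are merely inconclusive.

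**Working it through.** **1. Reproduce the plan's figure.** Section 8.2 gives 10 patients in stage 1, a stop at 0 or 1 responses, and 29 in total. It says "This study is designed to have an alpha of 0.0471, and a power of 80.5" per cent. The final cut-off is not stated. With success at s or more of 29,

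P(success | p) = Σ (x = 2 to 10) Bin(x; 10, p) × P[Bin(19, p) ≥ s − x].

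- s = 6: 0.0471 at p = 0.10 and 0.8051 at p = 0.30. Both stated figures are reproduced.
- s = 5 gives alpha 0.1016 and s = 7 gives 0.0177, so 6/29 is the implied cut-off.

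**2. The cut-off under section 8.3.2.** That section requires the Agresti-Coull lower 95% bound to exceed 10%. With ñ = 29 + 1.96² = 32.84 and p̃ = (x + 1.92)/32.84:

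- x = 6: p̃ = 0.241; lower bound 0.241 − 1.96 × √(0.241 × 0.759/32.84) = 0.095.
- x = 7: lower bound 0.120.

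This rule therefore needs 7/29.

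**3. How often the per-arm test misses a real increase over 10%.**

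| True ORR | Missed, ≥6/29 | Missed, ≥7/29 |
|---|---|---|
| 30% | 19.5% | 26.1% |
| 20% | 56.9% | 69.4% |

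A true ORR of 20% would arise if, for example, half the tumours convert and only those gain 20 points: 10% + 0.5 × 20 points. The converting share is my assumption; the documents give none.

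**4. What a null-looking result excludes.** Exact 95% intervals are 3.9% to 31.7% for 4/29 and 0.3% to 44.5% for 1/10, the latter being a stage 1 stop. Both contain the 30% target.

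**5. Whether 10% fits the endpoint.** Section 1.3.1.1 reports the earlier vorinostat-tamoxifen trial, without pembrolizumab: 19% objective response, and 40% for response or SD of at least 24 weeks. The second definition is the one close to this trial's ORR. Putting p = 0.40 into the formula in step 1 gives success 95% of the time (94% with ≥7/29). For the ER+ arms, passing or failing against 10% therefore says little about TIL. This comparison does not carry over to Arm C, which has no tamoxifen.

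**6. A contrast that would address TIL.** The plan does not specify one. Suppose response is compared between converters and non-converters by two-sided Fisher test at 5%, with 30% and 10% response. Assume everyone is biopsied and about half convert. Neither assumption comes from the documents, and section 3.1 admits some patients whose disease cannot be biopsied. Summing binomial probabilities over all significant tables:

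- One arm of 29: power 16% (14 non-converters, 15 converters) or 22% (15 and 14).
- All 87 pooled (43 non-converters, 44 converters): 57%; reversing the split gives 63%.

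**The case against.** The strongest reply is that the plan does have a reference. Section 8 states an expected rate of 10% or less without vorinostat and makes 10% the formal null, adding "We estimate that each regimen under evaluation will achieve ORR ≥ 30" per cent. Read that way, a matching increase in ORR means beating 10%, tested with 80.5% power. This stands as far as it goes: it would be wrong to say that there is no ORR to compare with, or that converters versus non-converters is the only contrast available. But the reference is assumed rather than concurrent, it fits the endpoint poorly (step 5), and the test asks whether a regimen beats 10%, not whether TIL drives response.

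A reader might also infer that the trial would miss a true TIL effect most of the time. The documents do not support that as a general claim. At the design effect the per-arm test misses about one in five, or one in four under section 8.3.2. The low-power figures in step 6 depend on a test that the plan does not state. If no increase means only that the observed rate in converters is no higher than in non-converters, the chance of wrongly seeing none with 14 non-converters and 15 converters is Σ Bin(x; 14, 0.10) × Bin(y; 15, 0.30) over y/15 ≤ x/14, which is 10.5%. The answer turns on what an increase means, and the rule does not say.

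Finally, the sentence is exploratory and no statistical section implements it. That is correct and limits the severity.

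**Conclusion.** The point holds in a limited form. Confident rejection is not supported, because the reference is an assumed 10% that does not match the endpoint, low and high TIL and the required increase are undefined, and no TIL–response test is specified or powered. Even on the reading kindest to the plan, a 20–26% chance of missing the full design effect, and intervals that still contain 30%, do not amount to confident rejection.

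The per-arm figures rest on the plan's own design and the implied 6/29 cut-off. The 57–69% miss rate holds only if the true ORR is about 20%. The converter contrast rests on assumed full biopsy coverage and about half converting, and incomplete biopsies would lower its power. Severity is minor: stopping, the primary endpoint and patient care are untouched.

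**What to change.** - Delete the rejection sentence from sections 2.3 and 2.5.
- Define low and high TIL before the data are examined.
- In section 8.3.4.1, report the response difference between converters and non-converters with a 95% CI, pooled and stratified by arm. Label it a hypothesis-generating association, since conversion is observed after treatment starts and is not randomised.
- State a meaningful difference in advance, for instance 20 points, the gap between the plan's 10% and 30%. Call the hypothesis unsupported only if the upper limit falls below it; otherwise report the result as inconclusive.

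Pooling matters here. With an assumed 20% response in both groups, the approximate CI half-width is 1.96 × √[0.16 × (1/43 + 1/44)] = 17 points for all 87 patients, but 1.96 × √[0.16 × (1/14 + 1/15)] = 29 points for one arm. A single arm could therefore rarely exclude a 20-point difference.

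The cost is wording and one extra estimate. The protocol gives up a claim that it cannot support, and must accept that the likely answer may be inconclusive.

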3.1 Characteristics

We propose a three arm, 20-87 patient trial in patients with hormone therapy resistant breast cancer to test the optimal sequence and dosing of epigenetic immune priming in hormone therapy resistant breast cancer. The two arms all include vorinostat, TAM and pembrolizumab to evaluate either sequential priming (Arm A) or, concurrent priming with maximal dosing of both epigenetic and immune modulators in ER+ (Arm B) and ER- (Arm C?) disease. Stage 1 of the trial will evaluate 20 patients, 10 in each arm and randomly assigned. If the response rates are adequate, the trial will proceed to Stage 2 in order to evaluate 58 patients, 29 in each arm.

Given the absence of responses in PD-L1 low patients to pembrolizumab, we will determine the benefits for vorinostat in reversing therapy resistance to pembrolizumab in ER-negative breast cancers (HER2-positive or negative)

Patients will be evaluated for response at 12 weeks by RECIST1.1 (using IR-RECIST) and will continue on therapy if they have stable disease or response at the time of disease evaluations. Patients with progression on imaging, but are clinically stable, may stay on study but will require follow up staging after 4-6 weeks. Patients will be assessed continually for safety and tolerability as well as for any adverse events. If progression on therapy with pembrolizumab, patient may continue if clinical indicated and be re-evaluated after 4-8 weeks.

We will follow AEs of clinical interest as defined by Merck and will dose modify pembrolizumab as per Merck guidelines. We have significant prior experience with vorinostat as an agent and are familiar with managing drug toxicities. In addition, we are experienced with immune-related toxicities as well.

Tissue biopsies of all patients will be collected prior to enrollment to assess for pre-treatment TIL and PD-L-1 expression. A limited number of patients with disease unamenable to biopsy will be allowed to enroll in the trial with prior approval from study PI. Follow up biopsies and peripheral blood collection will be taken from all patients post-treatment, prior to starting cycle 4, to characterize changes in local tissue effects and antigen-specific cellular and humoral immune responses in peripheral blood.

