3.2 Number of Subjects

20-87 patients

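### The stated range of 20-87 patients joins a two-arm minimum to a three-arm maximum; under Section 8 it is 30-87, and Section 3.1 gives Arm C no stage size or accrual gate

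*Combined protocol and SAP*

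**What the plan says.** Section 3.1 opens with "We propose a three arm, 20-87 patient trial". A few lines later it gives the stage sizes: "Stage 1 of the trial will evaluate 20 patients, 10 in each arm and randomly assigned", and then "If the response rates are adequate, the trial will proceed to Stage 2 in order to evaluate 58 patients, 29 in each arm". In the same paragraph Arm C appears only in brackets with a question mark after it, and no stage size is attached to it. Section 3.2 and the synopsis repeat "20-87 patients".

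Section 8.0 says "Three arms will be tested, with each independent assessment". The paragraph numbered 8.2 sets out the Simon design separately for each arm: "In the first stage, 10 patients will be accrued and a decision will be made to continue or stop accrual". Accrual to an arm stops at 0 or 1 responses in those 10; otherwise 19 more are added, for 29.

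Other places describe Arm C differently:

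- The synopsis design paragraph attaches the Simon design to a randomised two-arm trial in ER-positive patients and then adds Arm C for ER-negative patients.
- Section 2.4 describes "A comparator arm in ER-negative tumors with biomarker endpoints".
- Section 3.6 speaks of two arms under test and says that ER-negative patients need no randomisation.

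**The concern.** The two ends of a sample-size range should come from the same number of arms. Here the lower end and both stage totals look like two-arm figures, while the upper end looks like a three-arm figure, in a trial that calls itself three-arm.

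The planned size is a figure that readers of the plan rely on. Section 3 is also where they look for how many ER-negative patients will be enrolled and what would stop that enrolment, and Section 3.1 answers neither question. The answer has to be inferred from the per-arm wording in Section 8, and the synopsis, 2.4 and 3.6 leave room to doubt that this wording was meant to reach Arm C.

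**Working it through.** **Inputs.** Arms: three (3.1, 8.0), of which A and B are randomised and C is not (3.6). Per-arm design (8.2): 10 patients in stage 1, stop at 0 or 1 responses, otherwise 19 more for 29; null rate 10%, alternative 30%, one-sided; alpha 0.0471, power 80.5%. No dropout allowance is stated, so none is applied.

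**Step 1: reproduce the per-arm design.** With a final boundary r, the arm is declared active if stage 1 gives at least 2 responses and the total exceeds r:

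P(active | p) = Σ (x = 2 to 10) C(10, x) pˣ (1 − p)¹⁰⁻ˣ × P(Y ≥ r + 1 − x), with Y ~ Binomial(19, p).

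The text of 8.2 gives no r. Exact values are:

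| r | p = 0.10 (alpha) | p = 0.30 (power) |
|---|---|---|
| 4 | 0.1016 | 0.8369 |
| 5 | 0.0471 | 0.8051 |
| 6 | 0.0177 | 0.7389 |

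The row r = 5 returns the plan's 0.0471 and 80.5%. A search over two-stage designs with alpha at most 0.05 and power at least 0.80 also finds 1/10 then 5/29 as the optimal design. The per-arm figures are right, so any error lies in how arms are added up.

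**Step 2: total over arms.**

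| Arms counted | All stop at stage 1 | All go to stage 2 |
|---|---|---|
| Two (A + B) | 2 × 10 = 20 | 2 × 29 = 58 |
| One (C) | 10 | 29 |
| Three (A + B + C) | 30 | 87 |

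The stated 20 matches only the two-arm row, and so does 58. The stated 87 matches only the three-arm row. No single number of arms gives 20-87.

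**Step 3: does another reading of Arm C rescue the range?** Let Arm C contribute at least m and at most M patients, with A and B contributing 20 to 58. The total then runs from 20 + m to 58 + M. A lower end of 20 needs m = 0; an upper end of 87 needs M = 87 − 58 = 29. So 20-87 is coherent only if Arm C may enrol nobody and may also enrol 29. The documents do not say that Arm C is optional. If Arm C were an ungated cohort of fixed size 29, the range would be 20 + 29 = 49 to 87, and 20 would still be wrong.

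**Step 4: scope of 20 and 58.** Section 3.1 gives 20 as a figure for the whole trial and as randomly assigned patients. Because 3.6 exempts ER-negative patients from randomisation, the 20 can only be Arms A and B. The 58 is exactly twice 29, so it has the same scope. Arm C therefore has no stage number in 3.1.

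**The case against.** The best defence is that most of these figures are right for what they describe. For the two randomised arms, 20 and 58 are correct, and the reference to random assignment signals that scope. The maximum, which caps enrolment, is 87 in all three places. Section 8 is the statistical section, and it gives each arm both a size and a stopping rule, so silence in a design overview does not override it. The biomarker description in 2.4 does not exclude a response gate either, since an arm can have both.

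Most of this stands. It reduces the stage-total problem to a missing label and a missing Arm C entry. It does not rescue the lower bound, which is wrong for three arms unless Arm C may be empty.

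A reader might go further in two ways that the documents do not support:

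- **That Section 3.1 understates its own total by 29 (58 against 87).** It does not. Its opening sentence already gives 87 as the maximum, and 58 is the total for Arms A and B.
- **That Arm C could reach 29 patients with no futility stop.** One might then count 19 extra patients in the 74% of cases where a true 10% rate would have stopped the arm. The probability itself is correct: 0.9¹⁰ + 10 × 0.1 × 0.9⁹ = 0.736. But it is a property of the Section 8 design under the null hypothesis. The figure of 29 for Arm C comes only from Section 8, where the stop is attached to it. If Section 8 governs Arm C, the stop applies; if it does not, Arm C has no stated size. Neither reading gives 29 without a stop, so this is not the size of the error.

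**Conclusion.** The sample-size range is wrong at its lower end. Under Section 8 as written, the minimum is understated by 10 patients (20 instead of 30). The operating characteristics of each arm are unaffected. This rests on taking Section 8 literally, with three arms each under the Simon rule, and on there being no statement that Arm C may go unfilled.

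The second part is an unresolved scope question rather than a numerical error. Section 8 puts Arm C under the response gate, while the synopsis and 2.4 can be read as placing it outside. Sections 8.3.1 and 8.3.2 add to the doubt, because they define the efficacy population and the response-rate denominator by randomised patients, which taken literally leaves Arm C out. The documents do not settle which reading the sponsor intends, so the passages have to be reconciled. The correction is worth making because it concerns the planned size of the trial and is cheap, but it is a correction of consistency and not a flaw in the test.

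**What to change.** If Section 8 stands as written:

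- State 30-87 patients in the synopsis, 3.1 and 3.2.
- In 3.1, label 20 and 58 as Arms A and B (randomised), add 10 and 29 for Arm C (not randomised), and give 30 and 87 as the totals. Remove the question mark after Arm C.
- State in 3.1 that the Section 8 accrual stop at 0 or 1 responses in 10 applies to each arm, including Arm C.
- Align the synopsis design paragraph and 2.4 with this.

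This costs only wording in an amendment; enrolment under Section 8 does not change.

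If the sponsor instead intends Arm C as a biomarker cohort outside the Simon gate, Section 8 must say so and give Arm C its own sample size with a justification. The total must then be restated as 20 to 58 for Arms A and B plus Arm C's own number. That route needs a new sample-size rationale as well as new wording.
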